This study will be conducted in accordance with the International Conference on Harmonisation guidelines for Good Clinical Practice (ICH E6) and the Code of Federal Regulations on the Protection of Human Subjects (45 CFR Part 46). The statistical analysis plans will be consistent with guidances such as the CONSORT Statement [1] or STROBE Statement [2], ICMJE recommendations [3], the 2016 and 2019 statements of the American Statistical Association [4,5], and recommendations in Nature [6,7].¹ All personnel involved in the conduct of this study have completed human subjects protection training.

¹ [1] www.consort-statement.org [2] www.strobe-statement.org [3] www.icmje.org [4] Wasserstein RL, et al. (2016), The ASA's Statement on p-Values, *The American Statistician*, 70:2, 129-133 [5] Wasserstein RL, et al. (2019), Moving to a World Beyond $p < 0.05$, *The American Statistician*, 73:sup1, 1-19 [6] Amrhein, et al. (2019) Scientists rise up against statistical significance, *Nature* 567, 305-307 [7] Editorial (2019) It's time to talk about ditching statistical significance: Looking beyond a much used and abused measure would make science harder, but better. *Nature* 567, 283-283.

Abbreviations and Definitions of Terms

[Spell out any acronyms, abbreviations, or non-standard terminology. Delete this text and any entries below that are not used in your protocol.]

Abbreviation/Acronym	Definition
AE	Adverse Event/Adverse Experience
CI	Confidence Interval
CIOMS	Council for International Organizations of Medical Sciences
CONSORT	Consolidated Standards of Reporting Trials
CRF	Case Report Form
CRO	Contract Research Organization
DCC	Data Coordinating Center
DSMB	Data and Safety Monitoring Board
eCRF	Electronic Case Report Form
FDA	Food and Drug Administration
GCP	Good Clinical Practice
HIPAA	Health Insurance Portability and Accountability Act
IB	Investigator's Brochure
ICF	Informed Consent Form
ICMJE	International Committee of Medical Journal Editors
IDE	Investigational Device Exemption
IND	Investigational New Drug Application
IRB	Institutional Review Board
N	Number (typically refers to subjects)
NDA	New Drug Application
PHI	Protected Health Information
PI	Principal Investigator
QA	Quality Assurance
QC	Quality Control
SAE	Serious Adverse Event/Serious Adverse Experience
SD	Standard Deviation
SE	Standard Error
SOP	Standard Operating Procedures
STROBE	STrengthening Reporting of OBservational studies in Epidemiology
UP	Unanticipated Problem

1. Protocol Synopsis

Study Title	Reducing Binge Eating to Prevent Weight Gain in Black Women
Objectives	
Primary: Examine the feasibility and acceptability of a 6-month AAT + NUTR (N=48) intervention. AA women (BMI ≥ 25 kg/m²) with weekly binge eating episodes will be randomized to the AAT+NUTR (n=24) or wait-list control (n=24). The study will examine recruitment, retention, barriers to completion, satisfaction, and adherence.
 
Secondary: At 4 (end of treatment) and 6 months (follow-up), examine changes in (a) binge eating; (b) depressive symptoms; (c) dietary outcomes (e.g., overall energy intake, fat, fruit and vegetable intake); and (d) weight for participants in each group.
 
Tertiary/Exploratory: Conduct key informant interviews (n=15-20) with UNC Department of Family Medicine staff and participants to determine acceptability of the AAT intervention in the primary care setting.

Target Population	
Key Inclusion Criteria Individuals are eligible if they are non-Latino Black women, over 18 years of age, have a BMI ≥ 25kg/m², use a Bluetooth-enabled smartphone, report at least one binge eating episode weekly, and complete the screening.
 
Key Exclusion Criteria Individuals will be excluded if they are currently pregnant, in substance use treatment, involved in a weight loss program, have a history of anorexia nervosa, engage in purging, are currently receiving psychological or pharmacological treatment for disordered eating or eating disorders, or are concurrent intravenous drug users or consume >4 alcoholic beverages/day.

Numbers of Participants	
Number to be recruited for screening [some will not be eligible for enrollment] 200
 
Number of eligible participants enrolled [this is the target sample size for enrollment] 60

Clinical Phase	[I, II, III, or IV (if applicable)]
Intervention	
Participants will participate in an 16-week combined Appetite Awareness Training (AAT) + Diabetes Prevention Program (NUTR) intervention. For the first 8 weeks, participants will attend 8 weekly AAT sessions and then transition to eight, weekly NUTR sessions. All sessions will be 60-90 minutes. The goal of AAT is to enable participants to be able to relearn their stomach's hunger signals and begin to obey and monitor functions of satiety. AAT has been successful in helping participants diagnosed with eating disorders reduce binge eating, overeating, and prevent weight gain. Sessions involve didactic training, review of self-monitoring of eating episodes, and homework assignments. NUTR includes group sessions that are based on the Diabetes Prevention Program curriculum, and include content on nutrition (e.g.,

	shopping, fruit and vegetable intake, eating away from home), physical activity, and goal setting.
Study Description	
This study is a two-arm, randomized controlled trial to examine the feasibility and acceptability of 6 month AAT + NUTR compared to wait-list control. Patients will be recruited from the UNC Department of Family Medicine. AAT+NUTR participants will spend the first 2 months receiving treatment to reduce binge eating (AAT), and the next 2 months engaging in group-based nutrition counseling. Participants will then work independently for 2 months. Data from both intervention groups will be collected at 3 time points: baseline, before randomization (T1), at the end of month 4, post treatment (T2), and at the end of month 6, follow-up (T3). Descriptive analyses will first be performed overall, by treatment group, and time points to identify any data anomalies (e.g., missing data, outliers, non-normality) that may invalidate study findings. Remedial measures (e.g., single/multiple imputation of missing data, score/data transformation) will be applied as indicated based on the results of data screening.

Outcome Measures	
[Measures that will used to assess the intervention (for feasibility, tolerability, efficacy, safety, comparability, pharmacokinetics/pharmacodynamics, etc.)]
 
To assess the feasibility of recruiting adult, overweight/obese Black women to the proposed study, the percent of eligible overweight/obese black women who were enrolled and retained in the study will be examined and reasons for nonparticipation and attrition will be documented. Participants will also be asked to provide measurements for height/weight, blood pressure, binge eating, and complete several self-report measures.

Study Duration	2 years
Subject Participation Duration	30 hours
Estimated Time to Complete Enrollment	January 2019-July 2021
Statistical Analysis Plans	
[Feasibility will also be determined by calculation of point and interval estimates (95% confidence intervals using sample size methods) of the feasibility parameters (proportion/percentages in terms of eligibility, participation, retention; means/medians for attendance at intervention sessions) and bivariate frequency distributions. Linear mixed effects modeling will be used to predict the association between treatment group assignment (AAT + NUTR or control), and binge eating, dietary intake, and weight scores at T2 and T3. Baseline scores will be used as

	covariates in these analyses. Standardized mean differences (e.g., Cohen's d with bias adjustment) will also be calculated as an effect size measure with 95% CI.
--	---

2. Introduction: Background and Scientific Rationale

2.1. Background Information

[Do not copy the background section from a grant application. This protocol should reflect only information relevant to the current study, which may be smaller in scope than a grant award. The Background section should include a brief discussion of: the health problem the study will address (knowledge gaps); the name/description of the study intervention; prior research (in vitro, preclinical in vivo, and clinical trials) and experience that provides context and scientific justification for conducting the study; and the importance of the study. Include references in support of claims; in-text citations should be numeric in ascending order to match the reference list.]

Binge eating Disorder (BED) is defined as recurrent binge eating while concurrently experiencing loss of control, marked distress, and with the absence of compensatory behaviors for weight loss. BED is the most common eating disorder among all racial and ethnic groups, affecting approximately 2.6% of the US population. Moreover, BED is associated with other co-morbid conditions, including that substance disorders and mood disorders.

While there are several effective behavioral treatments for BED (e.g., Cognitive Behavioral Therapy (CBT), Interpersonal Therapy) there are racial disparities in treatment access. African-Americans (AA) have some of the lowest rates of access to care, and less than 8% of AA women with BED seek treatment compared to 20% of White women. Furthermore, BED may be more severe among AA women who DO not access treatment; for example, AA women receiving treatment for BED demonstrate less pre-treatment binge eating compared to non-treatment seeking controls with BED. Therefore, it is imperative that investigators develop strategies for treatments that are accessible and effective for AA women.

One strategy may be to intervene with women who have not yet developed BED, but who may show signs of early risk factors (e.g., binge eating, rapid weight gain). A possible group for early intervention may be AA women, particularly since more than 30% of this population reports binge eating. Though treatment seeking specific to disordered eating is disparate among AA women, there is ample evidence to suggest their willingness to participate in nutrition counseling and weight stabilization, particularly when delivered in primary care. Early detection and intervention with this population may be a critical first step to the prevention of BED, and the increase in treatment access for disordered eating behaviors.

Because AA women who binge eat may be at risk for BED, we hypothesize that by participating in a combined AAT+ nutrition counseling (NUTR) intervention, participants would increase awareness of BED risk, reduce binge eating, and stabilize weight. We also hypothesize this intervention will help reduce known co-morbidities, including depressive symptoms.

2.2. Supporting Pilot / Unpublished Data

[Provide essential details of any as-of-yet unpublished data used to justify the proposed study, including any adverse event data.]

Currently, intervention research addressing binge eating behaviors among AA women is extremely scarce. I am working to fill this gap. My pilot APPETITE study (n=31) examined the feasibility of Appetite Awareness Training (AAT), a CBT-intervention for binge eating, in a community-based sample of AA women (BMI=25-40 kg/m²) with moderately severe binge eating behavior. In this pilot study, retention was high (88%), and binge eating was significantly reduced at 8 weeks.

2.3. Scientific Rationale

[Describe and justify the selected intervention (including dosage, timing, schedule, method of administration, validity of scales, as applicable) and study population.]

Currently, 55% of Black women are obese. Obesity is a serious health problem with numerous co-morbidities. Recent evidence has encouraged investigators to focus their efforts on weight gain prevention in Black women. Consuming a healthy, energy-balanced diet and engaging in physical activity are important for prevention of weight gain. Black women, however, may be vulnerable to certain eating behaviors that may pose barriers to weight management. One particular barrier is binge eating, which is associated with severe obesity. By reducing binge eating episodes in black women, weight gain may be prevented. Based on our analysis, we determined that a sample of 60, evenly allocated between treated and control groups, is sufficiently powered (.80) to identify large standardized mean differences in binge eating ($d = .74$) (Aim #2). The sample, however, is underpowered to determine differences in weight. Because this study is exploratory, we are prioritizing feasibility, and an exploration of differences, rather than determining efficacy.

3. Objectives

The overarching goal of this research to examine the feasibility and acceptability of a combined AAT and NUTR intervention (N=48) in the primary care setting. Participants will be recruited from the UNC Department of Family Medicine, and will be randomized to a group-based 16-week intervention (8 weeks AAT + 8 weeks NUTR) or wait-list control. Following the end of the intervention, I will conduct semi-structured interviews with participants and primary care providers to determine the acceptability of the program.

3.1. Specific Aim 1

Examine the feasibility and acceptability of a 6-month AAT + NUTR (N=48) intervention. AA women (BMI ≥ 25 kg/m²) with weekly binge eating episodes will be randomized to the AAT+NUTR (n=24) or wait-list control (n=24). The study will examine recruitment, retention, barriers to completion, satisfaction, and adherence.

3.2. Specific Aim 2

4. At 4 (end of treatment) and 6 months (follow-up), examine changes in (a) binge eating; (b) depressive symptoms; (c) dietary outcomes (e.g., overall energy intake, fat, fruit and vegetable intake); and (d) weight for participants in each group.

5. Study Design

The proposed study will use a randomized controlled clinical trial design. A sample of 60 black women who report at least weekly binge eating episodes will be randomized to 2 arms of a 6-month AAT + BWL intervention: AAT+BWL or a control group. AAT+BWL participants will receive an 8-week AAT program, and an 8-week BWL program, both using a group format. Assessments will be conducted at 0, 4, and 6 months. This study will be conducted at one site: UNC Department of Family Medicine.

The goal of AAT is to enable participants to be able to relearn their stomach's hunger signals and begin to obey and monitor functions of satiety 11. AAT has been successful in helping participants diagnosed with Binge Eating Disorder (BED) and bulimia nervosa reduce binge eating, overeating, urges to eat in response to non-appetite stimuli, and prevent weight gain. 12-14 The AAT intervention includes eight 60-minute group sessions. All sessions involve didactic training, review of self-monitoring of eating episodes, interactive activities, and homework assignments to enable participants to practice learned skills. Participants will be provided a workbook, which will include session content, and self-monitoring forms.

The curriculum for BWL (behavioral weight loss) will be based on the evidenced-based curriculum from the Diabetes Prevention Program, or Prevent T2. Eight weekly session will review core content including healthy eating, increasing physical activity, and caloric balance. An outline of session curriculum is attached to the protocol.

[figure not shown]
Physical measures will be taken by trained staff, who will be supervised by [name], PI of this project. The following equipment will be used:

- 1. Height /Weight** will be measured on a digital scale and a wall-mounted stadiometer.
- 2. Waist Circumference** will be measured twice with a Gullick II measuring tape.
- 3. Blood pressure** assessment will be measured using an GE Dinamap Procure Auscultatory 400 Multi-Parameter Patient Monitor with the subject in a sitting position after at least a minute rest period.

Questionnaires:

- 1. Eating Disorder Examination (EDE-Q)** is a self-reported questionnaire based on the Eating Disorder Examination.
- 2. Beck Depression Inventory (BDI)24** is a 21-item questionnaire that measures symptoms and attitudes associated with depression.
- 3. Weight Efficacy Life-Style Questionnaire (WEL) 25:** The WEL is a 20-item questionnaire that assesses participants' level of confidence in resisting eating in varied situations and in different emotional states, with higher scores indicating more confidence.
- 4. Eating Disorder Examination – Overeating Section (EDE) 20** is a semi-structured interview to assess symptoms and DSM-IV diagnoses for Bulimia Nervosa, Anorexia Nervosa, and BED. Eating disorder symptoms are assessed on four subscales: restraint, eating concern, shape concern, and weight concern. The EDE has well-established validity, reliability, and has been used extensively as an established measure of disordered eating behavior.
- 5. Modified Sociodemographic Questionnaire** will be used to collect: age, marital status, education, neighborhood residence, employment status, household size, religious background, and income. Randomization will be performed by Microsoft Excel and the PI will be blinded to all randomization. A research assistant will be responsible for supervising randomization. Prior to randomization, potential participants will respond to flyers and will be screened to determine eligibility. If an individual is eligible, she will be given a date and time to meet with a research team member. Participants will be evaluated in person or by phone to determine the presence of at least one weekly binge eating episode using the overeating section of the Eating Disorder Examination. Participants will also complete anthropometric measurements, provide signed informed consent, and finish self-report measures. Once all baseline assessments are complete, participants will be randomized to the AAT + BWL intervention or control group. Participants will be assessed at 0, 4 months, and 6 months. Data on the AAT group will be collected at 3 time points: baseline, before randomization (T1); end of month 4, after the completion of intervention program (T2); and end of month 6, posttreatment follow up (T3). Data on the control group will be collected at: baseline (T1), 4 months (T2), and at the end of 6 months (T3).

Example #1 Flow diagram (e.g., randomized controlled trial). Customize to your study flow.]

5.1. Treatment Design

The proposed study will use a randomized clinical trial design. A sample of 48 Non-Latino, AA women (BMI ≥ 25 kg/m²; rationale: *prior clinical and research experience suggests that AA women within this BMI range are most likely to identify their eating as problematic and engage in a clinical intervention*²⁶) who report at least weekly binge eating episodes will be randomized to 2 arms of a 6-month intervention: **AAT + NUTR** or **wait-list control**. **AAT + NUTR** participants (n=24) will first receive a weekly, group-based AAT program for the first two months, and then will begin NUTR and receive weekly, group sessions for the next 2 months. **Wait-list control group** (n=24) participants will receive an abbreviated AAT treatment at the end of 6 months. Following the intervention, UNC WMP providers (e.g., social workers, preventive medicine residents), and participants will be asked to participate in a 30-60 minute interview on the acceptability of the AAT +NUTR program, and to explore factors that will increase dissemination and uptake in the primary care setting.

5.2. Experimental / Observational Design

The proposed study will use a randomized clinical trial design. A sample of 60 black women who report at least weekly binge eating episodes will be randomized to 2 arms of a 6-month AAT + BWL intervention: AAT+BWL or a control group. AAT+BWL participants will receive an 8-week AAT program, and an 8-week BWL program, both using a group format. Assessments will be conducted at 0, 4, and 6 months.

5.3. Measurement Design

Measure	Description	Assessment Schedule		
		Baseline	4 months	6 months
Eating Disorder Examination – Overeating Section (EDE) ³⁵	A semi-structured interview to assess symptoms and DSM-V diagnoses for Bulimia Nervosa, Anorexia Nervosa, and BED.	X	X	X
Modified Sociodemographic Questionnaire	A questionnaire to collect age, marital status, education, neighborhood residence, employment status, household size, religious background, and income	X		
Height /Weight	Will be measured on a digital scale and a portable stadiometer.	X	X	X
Eating Disorder Examination- Questionnaire (EDE-Q) ³⁶	A 41-item scale to assess disordered eating behaviors and attitudes.	X	X	X
Dietary Intake (e.g., overall energy intake, fat, fruit and vegetable intake)	Two-24-hr dietary recall interviews (telephone-based) will be conducted on randomly selected days during a 2-week period.	X		X
Beck Depression Inventory ³⁷	A 21-item instrument used for measuring attitudes and symptoms of depression.	X	X	X

5.4. Outcome Measures

Primary Outcome(s):

Table 2: Feasibility Measures (Aim #1) ³⁸	
Question of Interest	Feasibility Measures
Can we recruit our target population?	# of screened and eligible participants, and proportion of eligible screens who enroll
Will participants do what they are asked to do?	Adherence to study protocol (e.g. session attendance, homework completion)
Are the assessments too burdensome?	Proportion of planned assessments completed; duration of assessment visits
Will participants stay in the study?	% of study retention and reasons for dropouts
Is AAT + NUTR acceptable to study participants?	Semi-structured telephone interviews (n=15-20) will be conducted to receive feedback on intervention and suggestions for improvement.

Secondary Outcome(s): Linear mixed effects modeling will be used to examine the association between treatment group assignment (AAT + BWL or wait-list control group coded as a (0,1)-indicator) and binge eating, eating self-efficacy, depressive symptoms, weight, blood pressure, and waist circumference scores at 2 and 6 months.

6. Study Participants

6.1. Number of Participants

Number to be recruited for screening: 160

Number of eligible participants enrolled: 60

Eligibility criteria includes Non-Latino Black women individuals over 18 years of age, have a BMI ≥ 25 kg/m², use a Bluetooth-enabled smartphone, and report at least one binge eating episode weekly. We will recruit participants in two ways: 1) We will request an IRB-waiver to allow [name], the director of the Weight Management Program and co-investigator on this study to a list of eligible participants (e.g., Non-Hispanic, AA & White women, BMI > 30 kg/m²) at UNC Family Medicine. The names will be randomly ordered, and women will be sent an introductory letter via email and/or postal mail describing the project and inviting them to contact the research team if no further contact is desired. If no such contact is received, the letter will be followed by a telephone call from the project coordinator, who will discuss all components of informed consent and participation. 2) Potential participants will respond to flyers, email announcements in community centers, doctor's offices, churches, and university listservs. Participants will also be approached in local community agencies by community center staff members and lay health counselors to request their consent to be approached by a member of the research team. IRB-approved flyers will be posted in the lobbies and recreation halls of the community facilities. Potential participants may self-refer to the study after reading the flyer.

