6.2. Eligibility

Inclusion Criteria: In order to be eligible to participate in this study, an individual must meet **all** of the following criteria:

- Non-Latino Black women
- Over 18 years of age,
- Have a BMI ≥ 25 kg/m²
- Use a Bluetooth-enabled smartphone
- Report at least one binge eating episode weekly

Exclusion Criteria: Any individual who meets one or more of the following criteria will be excluded from participation:

- Individuals who are currently pregnant,
- In substance use treatment,
- Currently receiving psychological or pharmacological treatment for disordered eating or eating disorders,
- Children (under the age of majority for their location),
- Nonviable neonates or neonates of uncertain viability,
- Prisoners, other involuntarily detained or incarcerated (this includes parolees help in treatment centers as a condition of their parole),
- Decisionally impaired individuals,
- Children who are wards of the State (Foster children),
- Non-English-speaking individuals,
- People, including children, who are likely to be involved in abusive relationships, either as perpetrator or victim

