6.3. Strategies for Recruitment and Retention

Recruitment Strategy:

Using an IRB-approved waiver, a list of eligible participants (e.g., Non-Hispanic, AA women, BMI ≥ 25 kg/m²) at UNC Family Medicine will be generated from examining the electronic health record. We will then send an introductory letter via postal mail to all eligible participants. This letter will describe the study, and then provide information on opting out. Study staff will contact those who do not opt out and conduct an eligibility screen. If an individual is eligible, they will be given a date and time to meet with a research team member. Participants will be evaluated in person to determine the presence of at least one weekly binge eating episode using the overeating section of the Eating Disorder Examination. Participants will also complete height/weight measurements, provide signed informed consent, and finish self-report measures (See Table 1). Once all baseline assessments are complete, participants will be randomized to the AAT + NUTR intervention or wait-list control.

Retention Strategy:

Participants will receive \$25 for completing the assessment at 0, 4, and 6 months, for a total of \$75.00. Participants will be provided the incentive after participating in each assessment. If a participant withdraws prior to the completion of a particular assessment, the participant will only have access to incentives based on what assessments were previously completed. Because we wanted to prevent

coercion, we have purposely kept study incentives at a reasonable cost, and only at a level to offset the burden of participating in the study.

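### Sections 6.1 and 6.3 give different filters for the same Family Medicine record list, and only the 6.3 filter matches the eligibility criteria

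*Combined protocol and SAP*

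**What the plan says.** Section 6.1 opens with the eligibility rule: "Eligibility criteria includes Non-Latino Black women individuals over 18 years of age, have a BMI ≥ 25 kg/m²". The same paragraph then describes the first recruitment route, in which an IRB waiver gives access to a Family Medicine list of women described as eligible, with the example "e.g., Non-Hispanic, AA & White women, BMI > 30" kg/m². The listed women are sent a letter, and those who do not decline are telephoned.

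Section 6.2 requires every inclusion criterion to be met, among them "Non-Latino Black women" and "Have a BMI ≥ 25 kg/m²".

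Section 6.3, on recruitment strategy, again describes a waiver-based list at the same clinic, followed by a letter and a chance to opt out. Its filter is different: "a list of eligible participants (e.g., Non-Hispanic, AA women, BMI ≥ 25 kg/m²) at UNC Family Medicine will be generated". It continues: "Study staff will contact those who do not opt out and conduct an eligibility screen".

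Section 6.1 also has a second route that does not use the list. It covers flyers, email announcements, self-referral, and approach by community center staff and lay health counselors.

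The recruitment measures (5.4 and 9.1) are the counts screened and eligible, and the share of eligible screened women who enrol. Sections 9.1 and 10.3 add an eligibility percentage with a 95% confidence interval.

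**The concern.** The two filters differ on both race and BMI. White women cannot be an example of eligible participants in this trial, so the introductory abbreviation (e.g.) in 6.1 does not remove the conflict. Whoever prepares the waiver request or the record query from 6.1 would produce a different sampling frame from someone working from 6.3.

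The two errors in the 6.1 filter behave differently. Including women who cannot be enrolled costs effort and adds screen failures, but the later eligibility screen removes them. Leaving out Black women with BMI 25 to 30 cannot be repaired by a later screen, because those women are never contacted on this route.

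This matters because the primary aim is feasibility, the overarching goal in section 3 is set in primary care, and the record list is the plan's systematic route into that setting. The frame decides which population the Aim 1 eligibility percentage describes.

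**Working it through.** **1. The statements side by side**

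| Place | Race/ethnicity | BMI (kg/m²) |
|---|---|---|
| 6.1, eligibility sentence | Non-Latino Black | at least 25 |
| 6.2, inclusion criteria | Non-Latino Black | at least 25 |
| 6.3, record list | Non-Hispanic Black | at least 25 |
| 6.1, record list | Non-Hispanic Black and White | above 30 |

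The last row is the odd one out. Treating the two list descriptions as one list is an inference, but a strong one: same clinic, same type of waiver, and the same sequence of letter, opt-out and staff contact.

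**2. Who is affected if the 6.1 filter is run**

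- Black women with BMI from 25 up to and including 30 meet the BMI criterion but are not listed.
- White women with BMI above 30 are listed but cannot meet 6.2.
- Every woman reached through the list then has a recorded BMI above 30, so the clinic-recruited sample moves toward obesity.

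**3. Which Aim 1 measures move**

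Let S be the number screened, E the number eligible and M the number enrolled. Add W screened White women, all ineligible.

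- Number screened: S becomes S + W, which is larger.
- Eligibility percentage: E/S becomes E/(S + W), which is smaller.
- Share of eligible women who enrol: M/E stays M/E, because W enters neither term.

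M/E could move only if eligible women with BMI 25 to 30 enrol at a different rate from the others. The documents give no data on that.

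**4. Illustration of the eligibility percentage**

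The plan states no expected eligibility percentage. Its targets imply a yield of 60/160 = 37.5% from the figures in 6.1, or 60/200 = 30% from the synopsis. Take each in turn as the percentage e eligible among screened Black women. This supposes that every eligible woman enrols and that e does not depend on the BMI filter. Let w be the White share of those screened, which is an assumption because the documents do not give it. Then eligible/screened = e × (1 − w), and the screens needed for 60 eligible women = 60 / [e × (1 − w)], rounded up.

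| w (assumed) | e = 37.5%: eligible/screened | screens | e = 30%: eligible/screened | screens |
|---|---|---|---|---|
| 0% | 37.5% | 160 | 30.0% | 200 |
| 25% | 28.1% | 214 | 22.5% | 267 |
| 50% | 18.8% | 320 | 15.0% | 400 |
| 70% | 11.3% | 534 | 9.0% | 667 |

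**5. Illustration of the omission**

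Section 2.3 puts obesity at 55% of Black women and gives no overweight share. Assuming 20% to 30% are overweight, the part of Black women with BMI of at least 25 that a cut at 30 leaves out is:

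- 0.20 / (0.20 + 0.55) = 26.7%
- 0.30 / (0.30 + 0.55) = 35.3%

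These figures describe Black women in general. They do not describe this clinic or the subgroup with weekly binge eating. Section 2.3 links binge eating to severe obesity, so the part of truly eligible women left out may be smaller.

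**6. What does not depend on this point**

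The power statement in 10.6 reproduces: 30 per arm and d = 0.74 give power 0.805 with a two-sample t-test, at an assumed two-sided 5% level. The list filter is not an input to it.

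**The case against.** The strongest reply is that 6.3 is the dedicated recruitment section and already has a filter that agrees with 6.2, that both filters are given only as examples, and that enrolment is controlled by 6.2 and the eligibility screen. Much of this stands, and it rules out several stronger readings.

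- *The list is drawn with the wrong filter.* A reader of 6.1 alone might infer this. With 6.3 in view, the documents show an unresolved contradiction. They do not show which query will be run.
- *Women with BMI 25 to 30 could enter only by self-referral.* The second route in 6.1 also includes email announcements and active approach by community staff. The omission is confined to the record route.
- *The recruitment outcome as a whole is distorted.* The share of eligible women who enrol has only eligible women in its denominator, and adding ineligible women leaves it unchanged.
- *The trial comparison is biased.* White women cannot pass 6.2 and are not randomised, so contacting them does not touch the comparison between arms.
- *The loss is a known fraction.* The 27% to 35% range and the table by White share rest on assumed shares.

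It is also true that some ineligible women will be contacted under either filter, because weekly binge eating is established only at a later assessment. That does not excuse listing women whose ineligibility is already visible in the record, and it does nothing for eligible women who are never listed.

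**Conclusion.** The contradiction is real and sits in the current text. The list filter in 6.1 conflicts with the eligibility sentence in its own paragraph, with 6.2, and with the list in 6.3. The consequences are conditional on the 6.1 filter being run. In that case the number screened rises, the Aim 1 eligibility percentage falls for a reason unrelated to the target population, and the clinic-recruited sample shifts toward obesity.

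The size cannot be computed from the documents, because the clinic's racial and BMI mix is not given. The figures above are illustrations under stated assumptions. Confidence is high in the textual conflict and in the direction of these effects, and low in any particular magnitude.

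Section 8.2 adds a related conflict. It says that women identified from private records will not be approached directly unless they have agreed, and that participants will refer themselves. That does not sit with a list route in which staff telephone women who have not opted out.

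**What to change.** 1. In 6.1, replace the list definition with the one that agrees with 6.2 and 6.3: non-Latino Black women with a recorded BMI of at least 25 kg/m². Do this before the list is generated, and check that the waiver request carries the same filter.
2. Reconcile 8.2 with the list route in 6.1 and 6.3, so that the protocol gives one account of who may be contacted and on what basis.
3. If the 6.1 query has already been run, re-run it with the corrected filter. Report screening counts and reasons for ineligibility by recruitment route, and give the eligibility percentage among Black women with BMI of at least 25 alongside the total contacted. Removing White women from the denominator without reporting them would hide contacts that were made.

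The cost is a sentence in 6.1, a matching edit in 8.2 and a corrected record query. If the query has been run, add a second run and a screening table by route. No participants or study procedures are added.
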